Subjects will undergo study visits at the following times: preoperative data (2013-2017) out of patient records, postoperative Visit in the year 2018-2019 (1-6 years post XEN45 implantation).

2 patient groups will be analyzed separately: patients, who had a solo XEN procedure and patients, who had a combined XEN and cataract operation.

Study population general description

This study will include subjects presenting with open angle glaucoma and who meet the following inclusion and exclusion criteria. Any questions regarding a patient's eligibility should be discussed with the sponsor prior to enrollment.

An inclusion of both eyes of the same patient is possible.

Inclusion Criteria

1. Open Angle Glaucoma
2. History past XEN45 implantation with or without combined cataract procedure
3. Available preoperative endothelial cell count data not older than 1 year before XEN operation without any operation between the day of data record and XEN45 operation.
4. Age 18 years or older and of legal age of consent
5. Signed written informed consent
6. Availability, willingness, and sufficient cognitive awareness to comply with examination procedures

Exclusion Criteria

1. Patients with secondary IOP lowering procedures (excluding SLT, needlings, bleb revisions, YAG lasers, Argon lasers) after XEN implantation will be excluded from analysis, because the secondary IOP lowering procedures may influence endothelial cell count itself. Cataract operations without complications are no exclusion criteria, but have to be recorded.

Sample size determination and power analysis

No formal sample size calculation was done due to the unknown effect size.

Description of hypothesis for primary endpoint:

Null hypothesis: H0: the postoperative mean number of endothelial cells is lower than the preoperative.

Alternative hypothesis: H1: the postoperative mean number of endothelial is larger or equal than the preoperative

Study outcomes/endpoints

The primary endpoint is the change of central endothelial cell density compared to preoperative data.

Secondary objectives are the changes of supero-nasal and infero-temporal endothelial cell density compared to the central endothelial cell density, and pachymetry compared to preoperative data.

VI. Study Procedures

Slit lamp examination

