Data consistency was checked and data were screened for outliers and normal, Gamma, Log-normal and Tweedie distributions by using quantile plots. Continuous variables were also tested for these distributions by using Kolmogorov-Smirnov test. Depending on data distribution the following methods will be used: In case of parametrically testing, mixed models based on normal, Gamma and Tweedie distributions will be used to analyze data. Independent and unstructured working correlation matrices were used for modeling the corresponding covariance of Endothelial cell number over time. The model based estimator was used to estimate the covariance matrix. The corrected quasi likelihood under independence of model criterion will be used to select the final models. 95% confidence intervals will be computed for means and results will be illustrated by using Whisker plots. In case of nonparametrically testing, Wilcoxon's matched pairs test will be used. All reported tests will be done one-sided, and p-values < 0.05 were considered as statistically significant. All statistical analyses will be performed by use of STATISTICA 13 (Hill, T. & Lewicki, P. Statistics: Methods and Applications. StatSoft, Tulsa, OK) and NCSS 10 Statistical Software (2015). NCSS, LLC. Kaysville, Utah, USA.

IX. Literature Cited

2. Cairns JE. Trabeculectomy. Preliminary report of a new method. *Am J Ophthalmol* 1968;66:673-9.
5. Leske MC. The epidemiology of open-angle glaucoma: a review. *Am J Epidemiol* 1983;118:166-91.

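### The hypothesis is about a mean, but a look at the same data chooses between mean-based models and a rank test that does not test the mean when changes are skewed

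*Combined protocol and SAP*

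**What the plan says.** Section V (Study outcomes/endpoints) defines the endpoint without a summary measure: "The primary endpoint is the change of central endothelial cell density compared to preoperative data". The summary measure appears only in the hypothesis, in the same section: "H0: the postoperative mean number of endothelial cells is lower than the preoperative". The alternative is also written on the mean.

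Section VIII (Statistical methods) describes two screens. First, "data were screened for outliers and normal, Gamma, Log-normal and Tweedie distributions by using quantile plots". Second, "Continuous variables were also tested for these distributions by using Kolmogorov-Smirnov test". It then ties the method to the result: "Depending on data distribution the following methods will be used". The two branches are:

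- parametric: "mixed models based on normal, Gamma and Tweedie distributions will be used to analyze data", with the final model picked by a quasi-likelihood fit criterion;
- nonparametric: "In case of nonparametrically testing, Wilcoxon's matched pairs test will be used".

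Confidence intervals at 95% are planned for means. All tests are one-sided at 0.05. Section V adds that solo and combined procedures are analysed separately, that both eyes of a patient may be included, and that no sample size was calculated.

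**The concern.** The signed-rank test addresses the centre of the pairwise averages of the changes. This equals the mean when the changes are symmetric, but not in general when they are skewed. Skewed changes are also a natural reason for leaving a normal model. The primary result could therefore answer a different question from the stated hypothesis, and which question it answers would be settled after the data are seen.

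For a safety endpoint the direction matters. If a minority of eyes lose many cells, those eyes drive the mean and produce the skew, while ranks limit their weight. Section II gives some reason to expect uneven loss: with another tube device, the distance from tube tip to cornea was related to cell loss.

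The rule is also incomplete. It has no threshold, no named variable to screen, no primary method and no sensitivity analysis. Log-normal is among the distributions screened but has no model in the parametric branch.

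**Working it through.** The plan contains no power, SD or effect size, so there is no figure to reproduce. The check asks how far the two branches differ and when the rank branch would be reached.

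**Inputs from the documents:** up to 140 patients, two groups analysed separately (split not stated), one-sided 0.05.

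**Assumptions not in the documents:** SD of within-eye change 200 cells/mm²; 10% of eyes lose a further 800; no mean change in the rest; preoperative mean 2300 and SD 400 (needed only for screening levels); eyes independent. Tests are taken in the direction of loss. The printed H0 and H1 put loss under the null; that is a separate matter.

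**Step 1, the mean.** Mean change = 0.10 × (−800) = −80. Variance = 200² + 0.10 × 0.90 × 800² = 40,000 + 57,600 = 97,600, so SD = 312. Approximate power = Φ(√n × 80/312 − 1.645):

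- n = 70: Φ(2.14 − 1.645) = 69%
- n = 100: Φ(2.56 − 1.645) = 82%
- n = 140: Φ(3.03 − 1.645) = 92%

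**Step 2, the rank quantity.** The sum of two changes has within-component SD 200√2 = 283. Setting 0.81Φ(x/283) + 0.18Φ((x+800)/283) + 0.01Φ((x+1600)/283) = 0.5 gives x ≈ −83. The Hodges-Lehmann shift is therefore x/2 ≈ −42, about half the mean loss.

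**Step 3, simulation.** A range is the spread over repeated simulations. The fourth column is the Kolmogorov-Smirnov test of normality with fitted mean and SD (uncorrected) on paired changes. The fifth is the same test on pre- and postoperative levels.

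| n | Power, mean | Power, ranks | Normality rejected, changes | Normality rejected, levels |
|---|---|---|---|---|
| 70 | 70–72% | 39–41% | 27% | at most 0.2% |
| 100 | 84–85% | 49–52% | 52–54% | at most 0.2% |
| 140 | 93–94% | 60–61% | 76–78% | at most 0.4% |

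With the Lilliefors correction, rejection on changes at n = 100 rises to 96%.

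**Step 4, background loss.** If every eye also loses 50 cells/mm², power at n = 100 is 99.6–99.8% (mean) against 96.7–97.5% (ranks). At 100 cells/mm² both are about 100%.

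**Step 5, a different set of assumptions.** Here preoperative density has mean 2200 and SD 350, 10% of eyes lose about 40%, the rest have no mean change, and the SD of relative change is 5% or 10%. At n = 140 the mean change is −4.0% and the Hodges-Lehmann shift −1.1% or −2.0%; power is 99.5% or 93% (mean) against 62% or 60% (ranks). At n = 70 power is 87% or 65% against 39% or 38%. Under a uniform 5% loss the two methods agree on the estimate (both about −5%) and on power. The gap is therefore specific to concentrated loss.

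**The case against.** Several stronger readings are tempting, and the documents do not support them.

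- *Kolmogorov-Smirnov alone decides.* Section VIII names quantile plots first and adds the test to them, with no cut-off for either. The supportable statement is that the rule is unspecified.
- *The choice is a coin toss.* The figure near 50% holds only at about n = 100, only if paired changes are screened, and only for rejecting normality. The text mentions continuous variables, not changes. Gamma and log-normal distributions take only positive values, so listing them fits a screen of levels better, and on levels the switch hardly ever occurs. Rejecting normality also need not lead to ranks, because Gamma and Tweedie models, both mean-based, come first. None of the simulations models the plan's full sequence of choices.
- *The loss would be estimated by ranks and so reported too small.* Wilcoxon appears as a test only. The Hodges-Lehmann shift is a device of this check. The only planned estimates are means with 95% intervals, and that sentence is not expressly confined to the parametric branch.
- *The power gap is a property of this trial.* It rests on assumed values, including no loss at all in 90% of eyes one to six years after surgery, some of it combined with cataract surgery. A modest background loss removes most of it. The evidence in section II on tube position concerns another device and the implantation quadrant, whereas the primary endpoint is central density.

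All of this stands and limits the size of the concern. It does not remove the mismatch: the hypothesis is on the mean, and the stated rule can replace the test of that mean after the data are seen. That the switch rate runs from almost never to most of the time, depending on which variable is screened and which version of the test is used, shows how open the rule is.

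**Conclusion.** The concern holds in limited form. The primary method is data-dependent, and one branch does not test the quantity in the hypothesis when changes are skewed. If paired changes are screened and loss is concentrated in about 10% of eyes with none elsewhere, taking the rank branch costs roughly 30 to 35 percentage points of power for n between 70 and 140. With background loss of 50 cells/mm² or more in all eyes, little or nothing is lost at n = 100; if levels are screened, the rank branch is almost never reached. These sizes depend on the assumed SD, share of affected eyes and loss per affected eye. The mismatch itself does not. The change is worth making because it is cheap and the endpoint concerns safety.

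**What to change.** For the primary endpoint, delete the distribution-dependent choice in section VIII. State that the primary result in each group (solo and combined) is the mean paired change in central density, from one pre-specified model, with a 95% CI that allows for two eyes of one patient, whatever the distribution screen shows. A normal model with identity link, patient as cluster and robust standard errors would serve. Report Wilcoxon's matched pairs test as a sensitivity analysis only, noting that it treats eyes as independent. Use quantile plots of the paired changes for description.

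The cost is one paragraph of analysis-plan wording, with no new data or visits. The downside is slightly less power if the changes are symmetric and heavy-tailed; the rank result remains available in that case.

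### The plan permits an independence working correlation with only a model-based covariance estimator for paired pre/post counts; if that model is reported, the standard error of the primary change is wrong

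*Combined protocol and SAP*

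**What the plan says.** The endpoint is a within-eye comparison. Section V, Study outcomes/endpoints: "The primary endpoint is the change of central endothelial cell density compared to preoperative data". Section V also analyses solo and combined procedures separately, and under Study population general description it adds: "An inclusion of both eyes of the same patient is possible".

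Section VIII, Statistical methods, gives the parametric branch as "In case of parametrically testing, mixed models based on normal, Gamma and Tweedie distributions will be used to analyze data". It then describes the covariance with "Independent and unstructured working correlation matrices were used for modeling the corresponding covariance of Endothelial cell number over time", followed by "The model based estimator was used to estimate the covariance matrix" and "The corrected quasi likelihood under independence of model criterion will be used to select the final models". Neither working correlation is fixed in advance. No robust (sandwich) estimator is named, the cluster (eye or patient) is not defined, and the formula of the criterion is not given. Testing is set by "All reported tests will be done one-sided, and p-values < 0.05 were considered as statistically significant". The nonparametric branch is Wilcoxon's matched pairs test.

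The documents give no pre/post correlation, no SD and no share of patients with both eyes. They state that no formal sample size calculation was made.

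**The concern.** The text speaks of mixed models, but working correlations and a quasi-likelihood criterion belong to generalised estimating equations (GEE). On that reading, a model-based variance is valid only if the working correlation is right. Independence is implausible for two counts on the same cornea. Under independence, the variance of the change is the sum of the two visit variances, and the covariance that makes a paired design efficient is dropped.

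Two errors are then in play. Ignoring the pairing makes the standard error too large. Ignoring that some patients contribute two eyes makes it too small. The plan guards against neither and does not determine which standard error will be reported. What is at stake is the precision of the study's main result, in a study with no sample size calculation and two groups analysed separately.

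**Working it through.** **Inputs.** From the documents: a paired pre/post endpoint; both eyes allowed; 140 eyes; one-sided 0.05; cited tube-shunt losses of 11.5% and 12.4% (sections I and II). A preoperative count is an inclusion criterion, so an eye with a postoperative count forms a complete pair. Assumed, because the documents are silent: pre/post correlation rho; equal pre and post SD; share b of patients with both eyes in the study; correlation r of the change between fellow eyes. There is no figure in the plan to reproduce.

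**Step 1, pairing alone.** With n independent eyes, the independence model gives Var(change) = 2·SD²/n. The true value is 2·SD²·(1−rho)/n. The SE ratio is 1/√(1−rho):
- rho 0.3: 1/√0.7 = 1.20
- rho 0.5: 1/√0.5 = 1.41
- rho 0.7: 1/√0.3 = 1.83

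**Step 2, fellow eyes.** The share of eyes with a fellow eye in the study is s = 2b/(1+b). The true variance is multiplied by DE = 1 + s·r, so the net ratio is k = 1/√((1−rho)·DE). With b from 0 to 100% and r from 0.3 to 0.8, DE runs from 1 to 1.8. Size is P(Z > 1.645k). Power, for an effect that the correct SE detects with 80%, is P(Z > 1.645k − 2.487).

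| rho | k (DE 1.8 to DE 1) | one-sided size | power |
|---|---|---|---|
| 0.3 | 0.89-1.20 | 0.071-0.025 | 85-70% |
| 0.5 | 1.05-1.41 | 0.042-0.010 | 77-56% |
| 0.7 | 1.36-1.83 | 0.013-0.001 | 60-30% |

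The two errors cancel at rho = 1 − 1/DE, which is 0.44 at DE 1.8.

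**Step 3, does the criterion exclude independence?** With complete pairs, the eye as cluster and a time or time-by-group model, both structures give the same fitted means, so the criterion ties. In 200 simulated data sets (70 eyes, assumed SD 300, rho 0.7), point estimates and both common forms of the criterion agreed to rounding. The SE of the change was 50.3 under independence, 27.1 with correlation modelled and 27.4 robust. The ratio 50.3/27.1 = 1.86 is close to the 1.83 of step 1.

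The tie breaks with a covariate such as years since surgery, or with the patient as cluster. A form that penalises by parameter count then cannot favour the correlated structure, because the independence fit maximises the quasi-likelihood on which the criterion is built. In 2000 simulated data sets per rho it did so in 0%. A trace-penalty form picked independence in 19-32% of data sets with the covariate and in 34-36% with the patient as cluster.

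**Step 4, effect on a result (no fellow eyes).** A correct z of 2 (p 0.023) becomes 2·√0.5 = 1.41 (p 0.079) at rho 0.5, and 2·√0.3 = 1.10 (p 0.137) at rho 0.7.

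**Step 5, detectable change.** Assume 70 eyes per group and an SD of 15% of the mean. The independence SE is 15·√(2/70) = 2.54 percentage points; the true SE is 15·√(2(1−rho)·DE/70). The change detectable with 80% power is 2.487 × true SE under the correct analysis, and 1.645 × 2.54 + 0.842 × true SE under independence. Over DE 1 to 1.8:
- rho 0.5: 4.5-6.0% correct, 5.7-6.2% under independence
- rho 0.7: 3.5-4.6% correct, 5.3-5.7% under independence

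**Step 6, repairing the pairing only.** The ratio becomes 1/√DE. With 33-57% of eyes having a fellow eye in the study (b 20-40%) and r 0.3-0.6, DE is 1 + 0.33·0.3 = 1.10 to 1 + 0.57·0.6 = 1.34. The ratio is 0.95 to 0.86 and the size 0.058 to 0.078.

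**The case against.** The strongest reply is that this is under-specification and not a demonstrated wrong analysis. The harm needs three conditions: the parametric branch, a GEE fit despite the words about mixed models, and independence as the reported structure. The unstructured option, a true eye-level random-effect model and Wilcoxon's matched pairs test all keep the pairing, although run by eye they still ignore fellow eyes. Confidence intervals for the visit means do not carry the pairing error. All of this stands and limits the point. It does not remove it, because the plan names independence as an option and offers no valid rule for rejecting it.

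A reader might infer more than the documents support:
- *That the criterion will choose independence.* A tie chooses nothing, and the trace form picked the correlated structure in most simulated data sets. The plan does not say which form is meant.
- *That the SE is bound to be too large.* At low rho with many bilateral patients it can be slightly too small (0.89 at rho 0.3 and DE 1.8).
- *That a net ratio of 1.22-1.35 follows from rho 0.5.* Rho 0.5 alone gives 1.41. The narrower range also needs the fellow-eye assumptions of step 6.
- *That a serious loss would be missed.* Step 5 puts the detectable change well below 11.5-12.4%.

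The direction of harm also depends on the hypothesis. Section V states "Alternative hypothesis: H1: the postoperative mean number of endothelial is larger or equal than the preoperative". Under that wording an inflated SE makes a false conclusion of no loss less likely and a true one harder to reach. A missed modest loss arises only in a test directed at loss.

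**Conclusion.** The point holds, conditionally and with moderate weight. If the parametric branch is a GEE and the independence model is reported with its model-based SE, the precision of the primary change is misstated. At moderate or high rho the SE is too large: net 1.05-1.41 times at rho 0.5 and 1.36-1.83 times at rho 0.7, over the wide fellow-eye range. At rho 0.3 the error is smaller and can go either way (0.89-1.20). These figures rest on assumed rho, bilateral share, fellow-eye correlation and equal SDs. That independence is a listed option, and that the criterion cannot be relied on to exclude it, does not depend on those values. The practical cost is lost precision for modest changes.

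**What to change.** In section VIII, Statistical methods:
- State that independence with the model-based estimator will not be used for the primary change.
- Report a robust (sandwich) standard error clustered on patient, preferably with the unstructured pre/post correlation.
- Use the corrected criterion only to choose mean-model terms or the distribution, and give its formula.

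Make the pairing and patient-clustering changes together, because step 6 shows that repairing the pairing alone makes the test anti-conservative. A mixed model is a possible alternative, but its patient-level random effect must act on the change, since a patient intercept alone cancels out of it. That effect is informed only by patients with both eyes, and this route was not simulated.

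The cost is one or two sentences, with no extra data and no burden on patients. The robust estimator is marginally less efficient if the model is exactly right, and slightly liberal at this size: simulated one-sided size was 0.052-0.056 with 70 eyes from 56 patients, including runs with unequal SDs and an all-bilateral case.
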